24. A medication diary (paper) will be dispensed to the patient. Patient should record the date and time of medication intake at home for the 3 days prior to EoT, and for the previous day for all other clinic visits. Patients should bring the diary to the clinic for review. For more information, see section 4.1.4. If possible, a few days before the visit patients should be reminded (e.g., via telephone) to complete the medication diary, and to not take the study drug on the day of the study visit.
25. Patient will bring all the trial medication received directly from the central depot to the clinic for visit 2 (first dosing visit). Site will inspect all the trial medication and provide instruction to the patient on how medication is administered at home and how the medication should be brought to the clinic visits. Site will open the first bottle to administer the first dose in the clinic. When the patient is contacted after the trial medication is delivered to the patient's home (see footnote 23), they should be reminded to bring the trial medication to the clinic for visit 2. If possible, patients should be reminded (e.g. by telephone) to bring

Clinical Trial Protocol

Proprietary confidential information © 2025 Boehringer Ingelheim International GmbH or one or more of its affiliated companies

the trial medication to the clinic before each visit. Study visits will have to be rescheduled if trial medication is not available during the applicable visits. For information on how trial medication will be handled during the course of the trial, see section 4.1.4.

26. A separate eCRF will be used to collect specific data related to acute kidney injury (section [3.3.4.1](#)). After the FUP1 visit until the individual patient's end of trial only cancers of new histology and exacerbations of existing cancer, all trial drug related SAEs and all trial drug related AESIs will be collected (section [5.2.6.2.1](#)).
27. Medication compliance (section [4.3](#)) will be checked by capsule count by study site staff. For information on medication return, see [section 4.1.4](#).

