5.2.5 Other safety parameters

5.2.5.1 Ocular safety assessments

Eye exams including the evaluation of cataract by slit lamp will be performed by an ophthalmologist or an optometrist in both eyes to evaluate the presence of lens disorders and cataract during the screening period. Results from the eye exams must be available to the investigator before the patient is randomized in the IRT and trial medication shipment is initiated. The eye assessments will be repeated at EoT, and 30 days after last dose of trial medication (EoS) to monitor eye health and to observe any changes from baseline.

The eye exams do not have to be completed on the same day of the study visits. At study entry, eye exams can be completed during the screening period. For EoT and EoS visits, patients should try and complete the eye exams within the protocol allowed window (± 3 days) for the respective visits. Eye exams should be completed at the study site or at another healthcare or eye care facility.

Eye assessments will be performed according to the Eye Examination Worksheet provided by the sponsor. All cataracts will be graded using LOCS III. A copy of the worksheet will be available in the ISF. The results from the eye exams should be entered in a separate eCRF. Safety related findings will be reported as AEs if applicable. If documented medical history of cataract surgery in both eyes is available at the time of screening, eye assessments are not required, and patient will not undergo eye exams during the screening period, EoT, and EoS. If it is confirmed at the screening visit (by slit lamp exam) that the patient had cataract surgery in both eyes, eye assessments are not required at EoT and EoS.

Clinical Trial Protocol

Proprietary confidential information © 2025 Boehringer Ingelheim International GmbH or one or more of its affiliated companies

Patients participating in the trial remotely via the DCT model will complete the eye exams at a facility referred to by the investigator or patient could complete these exams at a local healthcare facility close to the patient's home. Results from the eye exams must be sent to the study site.

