5.2.6 Assessment of adverse events

5.2.6.1 Definitions of AEs

5.2.6.1.1 Adverse event

An AE is defined as any untoward medical occurrence in a patient or clinical investigation subject administered a medicinal product and which does not necessarily have to have a causal relationship with this treatment.

An AE can therefore be any unfavourable and unintended sign (including an abnormal laboratory finding), symptom, or disease temporally associated with the use of a medicinal product, whether or not considered related to the medicinal product.

The following should also be recorded as an AE in the CRF and BI SAE form (if applicable):

- Worsening of the underlying disease or of other pre-existing conditions.
- Changes in vital signs, ECG, physical examination and laboratory test results, if they are judged clinically relevant by the investigator.

If such abnormalities already exist prior to trial inclusion, they will be considered as baseline conditions and should be collected in the eCRF only.

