5.2.6.1.4 Adverse events of special interest

The term adverse events of special interest (AESI) relates to any specific AE that has been identified at the project level as being of particular concern for prospective safety monitoring and safety assessment within this trial, e.g. the potential for AEs based on knowledge from other compounds in the same class. AESIs need to be reported to the sponsor’s Pharmacovigilance Department within the same timeframe that applies to SAEs, see section [5.2.6.2.2](#).

The following are considered as AESIs:

Potential severe DILI

A potential severe Drug Induced Liver Injury (DILI) that requires follow-up defined by the following alterations of hepatic laboratory parameters:

- an elevation of AST and/or ALT ≥ 3 fold upper limit normal (ULN) combined with an elevation of total bilirubin ≥ 2 fold ULN measured in the same blood draw sample, or in samples within 30 days of each other, or
- ALT and/or AST elevations ≥ 10 -fold ULN.

These lab findings constitute a hepatic injury alert and the patients showing these lab abnormalities need to be followed up according to the “DILI checklist” provided in the EDC. In case of clinical symptoms of hepatic injury (icterus, unexplained encephalopathy, unexplained coagulopathy, right upper quadrant abdominal pain, etc.) without lab results (ALT, AST, total bilirubin) available, the investigator should make sure these parameters are analysed, if necessary in an unscheduled blood test. Should the results meet the criteria of hepatic injury alert, the procedures described in the DILI checklist should be followed.

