5.2.6.2 Adverse event collection and reporting

5.2.6.2.1 AE Collection

The investigator shall maintain and keep detailed records of all AEs in the patient files.

The following must be collected and documented on the appropriate CRF(s) by the investigator:

Clinical Trial Protocol

Proprietary confidential information © 2025 Boehringer Ingelheim International GmbH or one or more of its affiliated companies

- From signing the informed consent onwards until the follow-up visit: all AEs (serious and non-serious) and all AESIs.
- After follow-up-visit 1 until the individual patient's end of trial: cancers of new histology and exacerbations of existing cancer, all trial drug related SAEs and all trial drug related AESIs.
- After the individual patient's end of trial: the investigator does not need to actively monitor the patient for new AEs but should only report any occurrence of cancer and trial treatment related SAEs and trial treatment related AESIs of which the investigator may become aware of by any means of communication, e.g. telephone call. Those AEs should be reported on the BI SAE form (section [5.2.6.2.2](#)), but not on the CRF.

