7. PLANNED ANALYSIS

The individual values of all subjects will be listed, sorted by treatment group, subject number and visit (if visit is applicable in the respective listing). AE listings will be sorted by assigned treatment (see [Section 7.8.1](#), below for details).

For end-of-text tables, the set of summary statistics for non-PK parameters is:

N	number non-missing observations
Mean	arithmetic mean
SD	standard deviation
Min	minimum
Median	median
Max	maximum

For analyte concentrations, as well as for all PK parameters, the following descriptive statistics will additionally be calculated:

CV	arithmetic coefficient of variation
gMean	geometric mean
gCV	geometric coefficient of variation

The data format for descriptive statistics of plasma concentrations will be identical with the data format of the respective concentrations. The descriptive statistics of PK parameters will be calculated using the individual values with the number of decimal places as provided by the evaluation program.

Tabulations of frequencies for categorical data will include all possible categories and will display the number of observations in a category as well as the percentage (%) relative to the respective treatment group. Percentages will be rounded to one decimal place. The category missing will be displayed if and only if there are actually missing values. Percentages will be based on all subjects, in the respective subject set, whether they have non-missing values or not.

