Eye exams including the evaluation of cataract by slit lamp will be performed by an ophthalmologist or an optometrist in both eyes to evaluate the presence or absence of lens disorders and cataract during the screening period. Eye assessments will be performed according to the Eye Examination Worksheet provided by the sponsor. The individual ophthalmological values for all treated subjects will be presented via by-patient listing.

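### The released SAP plans only a by-patient listing for the eye exams, so lens changes have no by-arm summary of their own and the AE tables do not reliably supply one

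*SAP*

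**What the plan says.** Protocol 2.2.2.2 lists ophthalmological assessments among the safety endpoints. Protocol 5.2.5.1 schedules a slit-lamp exam of both eyes during screening, with cataracts graded by LOCS III, and repeats the assessment at EoT and EoS "to monitor eye health and to observe any changes from baseline". The same section links eye findings to AE reporting: "Safety related findings will be reported as AEs if applicable". Protocol 5.2.6.2.4 adds a separate eCRF for cataract.

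SAP 7.8.1 describes the exam in the screening period and then gives one output: "The individual ophthalmological values for all treated subjects will be presented via by-patient listing". SAP section 7 sets the order of listings: "The individual values of all subjects will be listed, sorted by treatment group, subject number and visit".

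The AE rules that bear on eye findings are these:

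- Protocol 5.2.6.1.1 makes recordable as an AE "Worsening of the underlying disease or of other pre-existing conditions".
- After follow-up visit 1 (FUP1), protocol 5.2.6.2.1 narrows collection to "cancers of new histology and exacerbations of existing cancer, all trial drug related SAEs and all trial drug related AESIs". Footnote 26 of Flow Chart A says the same.
- Protocol 5.2.6.1.4 opens its list with "The following are considered as AESIs" and names only potential severe drug-induced liver injury.
- SAP 7.8.1 counts AEs as on-treatment until 5 days after the last dose (the residual effect period, REP) and labels later ones post-treatment.
- Protocol 7.2.6 counts AEs up to end of study as treatment-emergent.

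**The concern.** Protocol 1.2 reports irreversible lens degeneration in rats that depended on dose and time. It also gives exposures that temper this. The lowest dose in the 26-week study, at 1X the human exposure expected with 80 mg daily, was free of lens findings. The threshold dose, seen in a 13-week study, was at 4X. Dogs showed no lens effects. The protocol still treats the risk as worth monitoring: it has an entry limit, a stopping limit, repeated exams and an ophthalmologist on the safety review committee.

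Exams are done by local ophthalmologists or optometrists, and the documents describe no central grading. Some grade shifts can therefore be expected in every arm, so the informative reading is each dose against placebo. A listing does not give that reading. No rule in the released text says what counts as a change, how two eyes combine into one patient, or who was not examined. At stake is whether the report states a by-arm result for the lens risk or leaves each reader to build one.

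**Working it through.** The plan states no figure on this point, so the check compares sections and then works out the timing.

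**1. Outputs for each safety endpoint in protocol 2.2.2.2**

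| Endpoint | Output in the released SAP |
|---|---|
| AEs, SAEs, AEs leading to discontinuation | Tables by treatment (7.8.1) |
| Laboratory tests | Number and percent with abnormal values (7.8.2) |
| Vital signs | Descriptive statistics (7.8.3) |
| ECG | Descriptive analysis plus listings (7.8.4) |
| Ophthalmological assessments | By-patient listing only (7.8.1) |

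**2. Which lens findings reach the by-arm AE tables?**

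- *Reported as an AE with onset on treatment:* yes. This includes a cataract found at the EoT exam and a worsened pre-existing one.
- *(a) Lens change not reported as an AE:* no. Reporting is conditional under protocol 5.2.5.1. The group is narrowed because entry is capped at NC1/NO1, C0, P0 (protocol 3.3.3, criterion 15). In a natural lens, any later cortical or posterior opacity, or a nuclear grade above 1, exceeds what the protocol accepts and is treated as cataract, which has its own eCRF. The released SAP names no table from that eCRF.
- *(b) Non-serious cataract first found at EoS:* unclear. It comes after general AE collection stops at FUP1 and is not an AESI. If reported with an onset after the REP, the SAP labels it post-treatment, and the released text names no table for that period. But protocol 7.2.6 runs to end of study, and an onset dated earlier than the exam could place the case on treatment.

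**3. Timing of the EoS exam**

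Inputs: EoT day 85, FUP1 day 92 and EoS day 115 (Flow Chart A); EoS eye exam 30 days after last dose, ±3 (protocol 5.2.5.1); REP 5 days. The last dose is taken to be on the EoT day.

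- REP ends: 85 + 5 = day 90.
- EoS after REP, nominal: 115 − 90 = 25 days.
- EoS after REP, range: (30 − 3) − 5 = 22 to (30 + 3) − 5 = 28 days.
- EoS after FUP1, nominal: 115 − 92 = 23 days.
- An EoT exam at the end of its ±3-day window is on day 88, before day 90, so inside the REP.

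Two post-dose exams are scheduled, and (b) concerns one of them.

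**4. What a by-arm table could show at the planned size (exact two-sided 95% limits)**

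- 0/15: upper limit 1 − 0.025^(1/15) = 21.8%.
- 2/15 = 13.3%: 1.7% to 40.5%.
- 0/45 (three active arms pooled, 3 × 15): upper limit 1 − 0.025^(1/45) = 7.9%.

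**The case against.** The strongest points on the other side:

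- **Nothing is lost.** Every eye value is listed and sorted by arm, so with about 15 patients per arm a reader can count. This stands, but the reader would have to supply the definition of change and the denominator.
- **Group (a) is small by design.** The entry cap and the cataract eCRF leave mainly shifts within the permitted nuclear range and findings judged not clinically relevant. Part of what the table counts will be grading noise. This stands as a limit on size, and it is also why placebo should be in the table.
- **EoS cataracts may be tabulated after all.** A reader might infer that they are shut out of the report. The documents do not support that: protocol 7.2.6 counts AEs to end of study, protocol 5.2.5.1 sends eye findings to AE reporting in the section that schedules the EoS exam, and onset can precede detection. They also appear in the listing. Equally, the collection limit and the SAP window make capture uncertain.
- **The SAP is not fully shown.** Pages within and after the safety section are missing, and the sponsor's standard tables and the committee's data review plan are not among the documents. Any of these could hold an eye table. The ocular paragraph itself shows no redaction.
- **Patients are watched.** The safety review committee sees individual and aggregated unblinded safety data (protocol 8.7). This lowers the risk during the trial but puts no by-arm result in the report.

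**Conclusion.** The point holds as a reporting gap, worth considering and cheap to close. On the released text, a named safety endpoint measured to detect change from baseline has only a listing. The AE tables cover lens findings reported as on-treatment AEs but do not reliably cover (a) or (b). The number of findings affected cannot be estimated from the documents.

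Two stronger readings should not be drawn. This is not a conflict between protocol and SAP: protocol 7.2.6 promises that other safety-relevant data will be assessed for change, not that a table will be made. Nor is it evidence that lens safety goes unmonitored or that data are discarded.

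The conclusion rests on three assumptions: no unshown page or standard table already gives the summary; the last dose falls on the EoT day (for the timing); and cataract is not on the sponsor's list of events that are always serious, which is not shown. A cataract on that list would be an SAE and, if drug-related, would still be collected after FUP1.

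**What to change.** In SAP 7.8.1, keep the listing and add one descriptive table by arm, plus pooled active:

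- Number and percent of patients with a new or worsened lens finding or LOCS III grade, from screening to EoT and from screening to EoS, regardless of AE reporting or the REP.
- Compare the same eye over time and count each patient once.
- Include a row for patients exceeding NC1/NO1, C0, P0, the stopping limit in protocol 3.3.4.1.
- Denominator: treated patients with a post-baseline eye exam and a natural lens in at least one eye. Show the number not examined per arm.

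The cost is one table from exams already scheduled, with no added visit and no protocol change. It assumes that grades and lens status are recorded per eye, which depends on a worksheet that is not shown. If they are not, report new or worsened cataract as yes or no. The table will be imprecise, and local grading will produce some shifts in every arm, so it should be labelled descriptive. If an unshown page already holds such a table, confirming that is enough.

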7.8.2 Laboratory data

The analyses of laboratory data will be descriptive in nature and will be based on BI standards (5). The number and percent of patients with abnormalities on treatment as identified by being outside the reference ranges for each laboratory parameter collected will be presented. The patients with possibly abnormalities/clinically significant abnormalities will be identified within the on-treatment period by study treatment.

Laboratory values will be summarized as frequencies of patients with abnormal values with patient individual listings.

A graphical summary highlighting potential cases of Hy's Law within each treatment group will be presented. The maximum on-treatment values of total bilirubin and ALT will be plotted each on a scale as multiples of the upper limit of normal. The figure will show areas that meet the criteria of cholestasis (total bilirubin $> 2 \times$ ULN), Temple's corollary (ALT $> 3 \times$ ULN) and Hy's Law as the combination of these two factors. A similar figure using maximum AST values in place of ALT will be constructed. An accompanying listing will show by sample date and study day the full course of the total bilirubin, direct bilirubin, ALT, AST and alkaline phosphatase values for patients whose total bilirubin are $> 2 \times$ ULN or AST or ALT values $> 3 \times$ ULN at any time during the study. The listing will indicate where the value meets the criteria, either falling in the cholestasis range, that for Temple's corollary or where the combination meets that for Hy's Law itself.

Laboratory data at unscheduled visits will be summarized in the listing: summary table for descriptive statistics will only include laboratory data from the scheduled visits.

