An electrocardiogram (ECG) analysis based on three Phase I trials in healthy volunteers (████████), (c█████0), and (████████) indicated that BI 764198 may cause QT prolongation in a dose-dependent manner for doses ≥ 80 mg BI 764198 once daily. After single and multiple doses of BI 764198, a reversible, dose-dependent increase of serum creatinine was observed in Phase I trials. It is believed that BI 764198 may increase serum creatinine by decreasing renal tubular secretion of creatinine via inhibition of renal transporters (e.g. MATE1) without an impact on kidney function as measured by unchanged cystatin C levels. Cystatin C (in addition to serum creatinine measurements) will be used to assess changes in renal function in patients treated with BI 764198.

Treatment in a proof-of-concept clinical trial 1434-0009 (████████) to reduce the risk/severity of acute respiratory distress syndrome in patients hospitalized for coronavirus disease 2019 (COVID-19) and requiring non-invasive oxygen therapy was terminated early, based on an independent data monitoring committee (DMC) recommendations, due to a clear lack of benefit in this critically ill patient population and a numerical imbalance of fatal events between the active and placebo treatment groups. Fatality rate was still within expected range for hospitalised COVID-19 patients on oxygen ([R20-3802](#)). Based on the totality of the data review from the study, BI has not identified to date any new safety risks for BI 764198. No adverse effects were noted to date which would impact the conduct of ongoing Phase 1 trials in healthy volunteers or the planning of Phase 2 proof-of-concept trials in chronic kidney disease (CKD).

Through favourable effects on glomerulosclerosis, delaying podocyte injury, and improving vascular function, a TRPC6 inhibitor may have the potential to slow disease progression when used on-top-of optimal therapy including ACEi/ARB. Such a therapy could be considered a notable advance in patient health and well-being by slowing progression to ESKD, improving clinical outcomes, reducing disease burden, and improving quality of life in proteinuric glomerular diseases such as FSGS.

For a more detailed description of the profile, refer to the current version of the IB (████████).

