12. Clinically significant laboratory abnormalities or medical conditions which pose a safety risk for the patient or may interfere with the trial objectives in the investigator's opinion (except for renal function tests or deviation of clinical laboratory values that are related to FSGS) at screening visit.
13. QTc intervals (QTcF) greater than 450 ms in males or greater than 470 ms in females, or any other clinically relevant ECG findings (at the investigator's discretion) at screening visit.
14. History of congenital long QT syndrome, previous drug-induced QT prolongation, or other risk factors for Torsade de pointes (e.g. hypokalemia, bradycardia, heart failure).
15. Detection of graded cataract by LOCS III higher than NC1/NO1, C0, P0 in the slit lamp eye examination at screening visit. Planned cataract surgery during participation in the study. Patients with cataract who have undergone lens replacement are not excluded.
16. A history of gastrointestinal (GI) surgery or GI disorders that could interfere with absorption of trial medication in the investigator's opinion.
17. Major surgery (major according to the investigator's assessment, e.g. hip replacement) performed 3 months before the screening visit or planned within 6 months after entering the study.
18. Any documented active or suspected malignancy or history of malignancy within 5 years prior to screening visit, except appropriately treated basal cell carcinoma of the skin or in situ carcinoma of uterine cervix.
19. History of relevant allergy or hypersensitivity according to the investigator's clinical judgment (e.g. systemic hypersensitivity reactions including anaphylaxis and anaphylactoid reactions to the excipients or any other systemically administered agent).
20. Patients who need to use restricted medications (section [4.2.2.1](#)) or any drug considered likely to interfere with the safe conduct of the study, e.g. drugs with known QT-prolongation effects.

Clinical Trial Protocol

Proprietary confidential information © 2025 Boehringer Ingelheim International GmbH or one or more of its affiliated companies

21. Patients not expected to comply with the protocol requirements or not expected to complete the study as scheduled (e.g. chronic alcohol or drug abuse or any other condition that, in the investigator's opinion, makes the patient an unreliable study participant).

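### The SAP 7.8.2 laboratory abnormality count ignores baseline, so for analytes often abnormal at entry it dilutes arm differences and misses worsening in patients already out of range

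*SAP*

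**What the plan says.** SAP 7.8.2 gives the "number and percent of patients with abnormalities on treatment as identified by being outside the reference ranges for each laboratory parameter". It adds that possible or "clinically significant abnormalities will be identified within the on-treatment period by study treatment", and that "Laboratory values will be summarized as frequencies of patients with abnormal values with patient individual listings". Neither category is conditioned on the patient's value before the first dose. The visible text names no shift table, change from baseline, or category for new or worsened abnormality.

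The section has other outputs: plots and a listing for potential Hy's Law cases, and a rule on unscheduled visits under which the "summary table for descriptive statistics will only include laboratory data from the scheduled visits". It opens by deferring to a sponsor standard (its reference 5), which is not in the text available for review.

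SAP 7 sets a general denominator for categorical tables: "Percentages will be based on all subjects, in the respective subject set, whether they have non-missing values or not".

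On the population, Protocol 3.3.2 requires UPCR of at least 1000 mg/g (criterion 4). Protocol 3.3.3 excludes eGFR only below 30 mL/min/1.73 m² (criterion 10), and its exclusion for clinically significant laboratory abnormalities applies "except for renal function tests or deviation of clinical laboratory values that are related to FSGS" (criterion 12). On the drug, Protocol 1.2 reports that "a reversible, dose-dependent increase of serum creatinine was observed in Phase I trials".

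**The concern.** An on-treatment yes/no count works when most patients start in range, because an abnormal value is then probably new. This trial selects patients whose kidney-related values are expected to be abnormal before dosing. For those analytes the count mixes abnormality that patients bring into the trial with abnormality that arises on treatment, and it cannot move when a patient goes from abnormal to more abnormal.

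The renal analytes are also those for which the protocol already reports a drug effect, the dose-dependent creatinine rise. Under Protocol Table 5.2.3: 1, creatinine results go to the investigator only up to visit 2. Investigator-reported laboratory adverse events are therefore an unlikely backstop for creatinine, and the analysis tables have to carry it.

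**Working it through.** The plan states no figure for this point, so there is none to reproduce. The check has two parts: a comparison of the text, then an illustration.

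**Text.** The SAP uses baseline in neighbouring sections but not in this one.

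- SAP 6.7 defines a baseline for endpoints not taken from 24-hour urine: the last measurement before the first dose.
- SAP 7.8.1 builds the adverse event analysis on treatment emergence.
- SAP 7.8.3 assesses vital signs for change against pre-treatment findings.
- SAP 7.8.2 states no such comparison for laboratory values.
- SAP 7.1 plans a screening category for serum albumin below 30 g/L, so low albumin at entry is anticipated.

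**Illustration.** Inputs:

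- n = 15 per arm (Protocol synopsis).
- q = share of patients out of range at baseline, taken to remain so on treatment. The documents do not give it, so it is varied from 0 to 1.
- r = rate of new abnormality among patients in range at baseline, assumed 50% on drug and 10% on placebo.

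Formulas:

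- Probability of being counted abnormal = q + (1 − q) × r
- Visible gap = (1 − q) × (0.50 − 0.10) = 0.40 × (1 − q)
- Gap in patients = 15 × visible gap
- Patients per arm who can become newly abnormal = 15 × (1 − q)

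Example at q = 0.6: drug 0.6 + 0.4 × 0.5 = 0.80; placebo 0.6 + 0.4 × 0.1 = 0.64; gap 16 points; 15 × 0.16 = 2.4 patients.

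The last column is the exact binomial chance that the drug arm shows at least 3 more abnormal patients than placebo, with independent arms of 15.

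| q | Drug | Placebo | Gap (points) | Gap (patients) | In range at baseline, per arm | Chance of ≥3 more on drug |
|---|---|---|---|---|---|---|
| 0 | 50% | 10% | 40 | 6.0 | 15 | 94% |
| 0.4 | 70% | 46% | 24 | 3.6 | 9 | 67% |
| 0.6 | 80% | 64% | 16 | 2.4 | 6 | 49% |
| 0.8 | 90% | 82% | 8 | 1.2 | 3 | 24% |
| 0.9 | 95% | 91% | 4 | 0.6 | 1.5 | 8% |
| 1 | 100% | 100% | 0 | 0 | 0 | 0% |

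**What each alternative recovers.** Restricting the count to patients in range at baseline keeps the expected gap at 40 points for any q below 1, but on only 9, 6 or 3 patients per arm at q = 0.4, 0.6 or 0.8. It also drops the patients whose worsening the present count misses. A low/normal/high shift table keeps them but scores high to higher as no change. Only change from baseline uses every measured patient and registers that worsening.

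**The case against.** The strongest reply is that the count is one output among several. SAP 7.8.2 refers to a descriptive-statistics table for scheduled visits, and SAP 7 defines such summaries as N, mean, SD, minimum, median and maximum. Protocol 7.2.6 calls for both quantitative and qualitative laboratory analysis, with arms compared on distribution parameters. A creatinine rise could appear in means and medians by arm whatever share began out of range. This stands, with a limit: the SAP mentions that table only when dealing with unscheduled visits and does not say that it includes change from baseline.

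Worsening is also partly covered elsewhere. Urine protein is the efficacy outcome, with change in UPCR analysed by ANCOVA (SAP 7.4.1). Acute kidney injury includes a rule of cystatin C at least 1.5 times baseline (Protocol 3.3.4.1) and has a separate eCRF (Protocol 5.2.6.2.4). Protocol 1.2 attributes the creatinine rise to reduced tubular secretion, with cystatin C unchanged. All of this stands. It narrows what could be missed, although the kidney injury rule would not describe a creatinine shift.

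The sponsor standard may already contain baseline-referenced tables. That can be neither confirmed nor excluded, and the absence of reference 5 from the available text is not counted as an error.

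A reader might infer more: that the table cannot show a drug effect, that a real signal is masked, or that this is the main laboratory safety display. The documents do not support these readings. The table is fully blind to new abnormality only when every patient is abnormal at baseline. Even at q = 0.8, if every remaining drug patient and no placebo patient became abnormal, the table would show 15/15 against 12/15, or 100% against 80%. For analytes mostly normal at entry, the randomised comparison with placebo remains informative. No section ranks this table above the others.

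The all-subjects denominator is a general SAP convention rather than a fault of this section. It matters here only in that a patient with no value counts as not abnormal.

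**Conclusion.** The point holds in limited form. As written, the count is not referenced to baseline. For analytes often abnormal at entry it dilutes a difference between arms in proportion to 1 − q, and it cannot show worsening in patients who are already out of range.

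The size depends on assumed values. With new-abnormality rates of 50% and 10%, a 40-point gap becomes 24, 16 or 8 points at q = 0.4, 0.6 or 0.8. That creatinine, cystatin C and albumin are often abnormal at entry is inferred from the entry criteria and the planned albumin category. For urine protein, q should be close to 1 if UPCR of 1000 mg/g or more lies outside the laboratory's range.

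This is a worthwhile correction to a descriptive safety display. It does not affect the primary endpoint, and it does not show that a signal would go undetected across all the planned outputs.

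**What to change.** In SAP 7.8.2, using the SAP 6.7 baseline, specify in this order:

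1. Change from baseline by arm and visit for creatinine, cystatin C, albumin and other analytes commonly abnormal at entry.
2. Shift tables from baseline category to worst on-treatment category.
3. New abnormalities on treatment, with measured patients who were in range at baseline as the denominator.

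Keep the existing out-of-range count as a secondary table. If the sponsor standard already supplies these outputs, one sentence citing the relevant part is enough.

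The cost is SAP wording and a few extra standard tables. No new data, visits or design changes are needed.
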